3.3 Study Duration

Subjects will be followed for a period of five years post-operatively.

3.4 Study Procedures

All parents or legal guardians of subjects must give their written informed consent in accordance with the informed consent regulations in Title 21 of the Code of Federal Regulations, Part 50. All subjects must give their written informed assent.

3.4.1 Subject Screening

Subjects will be recruited from among individuals referred to NYU Langone Weight Management Program for weight loss procedures. Both parents and children will be actively involved in the subject screening process. The information obtained from the parents will be about the child with minimal information on parent's weight history and family eating habits. Medical, social, psychiatric history and current psychological status, as well as weight history and eating disorders will be included in the subject screening.

3.4.2 Quality of Life and Psychological Evaluations

As part of the educational program, subjects and their parents will have visits with a nutritionist and psychologist before the surgery and at each follow-up visit (as listed below) after the operation, so they can be advised on dietary habit changes that will be needed. These scheduled visits will consist of an initial parent interview, initial child interview, questionnaires for the child assessing eating habits, degree of depression, degree of anxiety, subjective assessment of quality of life, body image satisfaction, self-esteem, and family environment. The parents will also be evaluated at scheduled follow-up visits with questionnaires assessing quality of life and family environment perceptions. Psychiatric Status will be evaluated by child study center psychologist with the use of an interview, a child behavior checklist (parent and self-report), a youth evaluation scale (parent and self-report), a three-factor eating questionnaire, and a child depression inventory.

Child Behavior Checklist (CBCL)

The Child Behavior Checklist (CBCL) is a device by which parents or other individuals who know the child well rate a child's problem behaviors and competencies. This instrument can

either be self-administered or administered through an interview. The CBCL can also be used to measure a child's change in behavior over time or following a treatment. The first section of this questionnaire consists of 20 competence items and the second section consists of 120 items on behavior or emotional problems during the past 6 months. The target age group of the test is 6 through 18 years old. Criterion validity was assessed and found to be acceptable.

The Youth Evaluation Scale (Y.E.S.)

The Youth Evaluation Scale (Y.E.S.) is a biopsychosocial assessment instrument for weight-related problems of boys and girls 12 to 20 years of age. Y.E.S. is designed for individual assessment and is a valuable component of the assessment of bulimia and anorexia nervosa. Subscales include physical, behavioral, fitness, depression, anxiety, self-esteem, family system, communication, and knowledge. Y.E.S. includes questionnaires for the adolescent and parent(s). Answers to over 600 questions are compared to established norms in each subscale. The analysis generates the Y.E.S. provider's summary report which presents historical, sensitive and specific information to the clinician. A separate Y.E.S. results report is also generated for parent(s) and adolescent education. Follow-up questionnaires and data summaries support the evaluation of post-treatment and long term changes. Using Y.E.S. involves administering the questionnaires to the adolescent and parent(s) and collecting data on weight, height and triceps skinfold.

Child Depression Inventory (CDI)

The CDI is a self-report, symptom-oriented scale which requires at least a first grade reading level and was designed for school-aged children and adolescents. The CDI has 27 items, each of which consists of three choices. The child or adolescent is instructed to select one sentence for each item that best describes him or her for the past two weeks. Quickscore™ form scoring makes the inventories easy and economical to administer. The CDI profile contains the following five factors plus a total score normed according to age and sex: negative mood, interpersonal problems, ineffectiveness, anhedonia, and negative self-esteem. The assessment is designed for a variety of situations, including schools, child guidance clinics, pediatric practices, and child psychiatric settings.

Three-Factor Eating Questionnaires

51-item three-factor eating questionnaire is to measure three dimensions of human eating behavior; (1) 'cognitive restraint of eating', (2) 'disinhibition' and (3) 'hunger'.

(See Table I)

3.4.3 Baseline Evaluations

- Height and weight
- Blood pressure
- Baseline laboratory
 - Metabolic profile (Sodium, Potassium, Chloride, CO₂, BUN, Creatinine, Glucose, Calcium)
 - Hematologic profile (Hemogram)

- Thyroid panel (T₃, T₄, TSH, Free T₄)
- Lipid panel (Total cholesterol, LDL, HDL, Triglycerides)
- Hepatic function panel (Albumin, Alkaline Phosphatase, Total Bilirubin, Direct Bilirubin, ALT, AST, Total Protein)
- HbA1c and Insulin
- Nutritional panel (Iron, Folate, B12, Vitamin D 25-Hydroxy, PTH, Magnesium, Phosphorus)
- OGTT (Oral Glucose Tolerance Test) (excluding subjects who have Type I or II diabetes)
- Urinalysis
- Bone density
- Chest x-ray
- EKG
- Gall bladder ultrasound
- Serum pregnancy test (for female subjects)
- Pulmonary Function Testing (if indicated by history and physical)
- Sleep study (if indicated by history and physical)

Gastrointestinal evaluation will include:

- Esophagram
- Esophageal manometry, (if necessary, to evaluate for esophageal dysmotility if patient presents with dysphagia and abnormal esophagram indicating achalasia)

Nutritional evaluation will include:

- Initial nutritional assessment
- Follow up nutritional assessment

Psychiatric evaluation will be evaluated by:

- Psychiatric Assessment
- Child Behavior Checklist (parent and self-report, attached: Appendix C)
- Youth Evaluation Scale (parent and self-report, attached: Appendix D)
- Child Depression Inventory (CDI, attached: Appendix A)
- Three-Factor Eating Questionnaire (attached: Appendix B)
- SF-36 Health Survey (attached: Appendix E)

3.4.4 Surgery

Subjects and parents will be required to attend an intensive pre-op assessment by the bariatric team at NYU prior to the operative procedure. Placement of the Lap-Band System will be performed laparoscopically and with the patient under general anesthesia. Placement of the Lap-Band via laparotomy will be performed only in cases where conversion is needed. The surgery will be done on an inpatient or outpatient basis. All patients will receive prophylactic antibiotics.

3.4.5 Follow-Up Visits

3.4.5.1 Scheduled Visits

Study data will be collected at 1-2 week, 6 weeks, 3 months, 6 months, 9 months, 12 months, and every 6 months thereafter for a total of five years. Subjects will be weighed and given a physical examination. Parents and subjects will meet with the nutritionist at these same visits.

The subjects will maintain the behavior modification program worked out with the nutritionist and psychologist before surgery. These programs are individualized to each subject's dietary habits, eating habits, and quality of life issues. The subject will be encouraged and counseled to combine their Lap-Band tool with long-term modifications in their lifestyle, including exercise. Weight loss, status of pre-operative comorbidities and development of complications will be reviewed at every follow-up visit. This will include testing to follow pre-operative comorbidities. Baseline laboratory and nutritional parameters will be repeated every 3 months for the first year post op. OGTT will be performed at 1 year and 5 year on the subjects who have impaired glucose tolerance at baseline testing (excluding subjects who have type I or II diabetes who is not clinically safe to perform the test). However, if the HbA1c or fasting blood glucose tests show abnormal results or the subject develops polyuria or polydipsia, additional interval testing should be performed based on ADA guidelines.

All laboratory, gastrointestinal, EKG, nutritional, and psychiatric evaluations which were performed at baseline will be repeated every 12 months.

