3.4.5.2 Band Adjustments

Fluid will be added to or removed from the band as indicated by the clinical progress, physical examination, and esophagram done at follow-up visit.

The adjustments will be performed as per study device manufacture's DFU.

Visits for band adjustments can also be initiated by the patient or their course between scheduled visits. If they lose weight too quickly; develop symptoms such as heartburn, nausea, vomiting or overeating; or develop a condition or illness requiring them to eat more, they will be evaluated for removal of fluid from the band. If they lose weight too slowly or overeat, they will be evaluated for addition of fluid to the band. Each evaluation will involve review of their clinical progress, physical examination, and esophagram if necessary.

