3.7.2 Secondary Efficacy Variable(s)

The secondary variables for evaluation are:

- Body mass index (BMI)
- Status of co-morbidities
 - Diabetes Mellitus or Impaired Glucose Tolerance
 - Hypertension
 - Asthma
 - Obstructive sleep apnea
 - Dyslipidemia
 - Gastroesophageal reflux disease
 - Urinary stress incontinence
 - Depression
 - Osteoarthritis
 - Back pain
 - Dyspnea and respiratory abnormalities
- Quality of life scores, depression degree, psychiatric evaluation

In general, the status of the comorbid conditions will be classified as unchanged, improved, resolved, or worsened. For the analysis of change in comorbidity status by the McNemar test, unchanged or worsened will be grouped into one category and resolved or improved will be grouped into a second category. For diabetes, this means whether there is change in serum HbA1c, insulin, OGTT, or fasting serum glucose or the amount of medication or no need for medication,. For hypertension, this means whether there is change in blood pressure or the amount of medication or no need for medication. For asthma, this means whether there is change in the amount of medication or no need for medication. For sleep apnea, this means

whether there is change in the sleep apnea study or a normal sleep apnea study. For hyperlipidemia, this means whether there is change in the lipid panel or the amount of medication or no need for medication. For gastroesophageal reflux, this means whether there is change in an annual esophagram or their symptoms. For urinary stress incontinence, this means whether there is change in clinical symptoms. For depression, this means whether there is change in the amount of medication or no need for medication or specified psychiatric evaluations.

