3.7.6 Statistical Methods

Change in the primary efficacy endpoint, % EWL, will be evaluated by a linear modeling in which the covariance among repeated measures of weight loss from month 6 to month 60 is

modeled. SAS PROC MIXED will be used in which two covariance structures will be examined by means of a REPEATED statement: unstructured (UN) and autoregressive (AR(1)). AIC will be examined to determine the most suitable structure. In the case that AR(1) is selected, a RANDOM statement for Subject will be included in the model. The predictive variable of greatest interest in the model is time. % EWL is expected to increase after surgery, more quickly initially, and then more slowly. To test for this decelerating trend, Time will be log transformed. The residuals of the model will be examined, especially those relative to predicted weight loss over time to ensure that the model is not over or under predicting over the course of follow-up. Systematic departures of the residuals from the predicted time course may require adding a quadratic trend to the model or the choice of a different transformation for time. Covariates used in the model will include baseline weight (as measured by BMI).

The null hypothesis is that % EWL will remain unchanged (i.e., at zero) post surgery. The alternate hypothesis is that % EWL will be positive post surgery. An alpha of 0.05 will be used to determine if the null hypothesis is rejected. The form of the weight loss over time is not part of the hypothesis of the study, but instead is included to better understand the expected trend weight loss follows.

The secondary efficacy endpoint, BMI, will be tested using a model similar to that used to test % EWL. The covariance structure selected for the modeling of % EWL will be applied in the modeling of BMI. Similarly, the same transformation of time will be applied to this endpoint. Baseline BMI will not be included as a baseline covariate, but instead will be assigned a value of time 0 and will be included as an endpoint measure. The null hypothesis is that BMI will show no change from time of surgery. The alternate hypothesis is that BMI will decrease after surgery.

The secondary efficacy endpoint of change in co-morbidities will be examined by McNemar tests. The null hypothesis is that there is no change in each co-morbidity post surgery. The alternate hypothesis is that there will be a change in each co-morbidity.

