13	Items monitored post op – 3 months, 6 months, 9 months, 12 months, 18 months, 2 years, 2.5 years, 3 years, 3.5 years, 4 years, 4.5 years, 5 years a) Height b) Weight c) BMI d) EKG (if data exists) e) Cardiac ECHO f) Fasting glucose (yearly only) g) Fasting insulin (yearly only)	k) Nutritional Panels (if data exists) l) Quality of life evaluations (if data exists) m) Depression questionnaire (if data exists) n) GTT (yearly only) o) LFT's (yearly only) p) Lipids (yearly only) q) Nutritional Panels (if data exists) r) Quality of life evaluations (if data exists)

	
 h) GTT (yearly only) i) LFT's (yearly only) j) Lipids (yearly only) 	
 s) Depression questionnaire (if data exists)
14	Healthcare issues post op 
 a) Hospitalizations b) Operations c) New medical problems 	
15	Post op care (if data exists) 
 a) Scheduled visits to weight management program – each year b) Unscheduled visits to weight management program – each year c) AGB adjustments – each year

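### The comorbidity analysis in 3.7.2 and 3.7.6 cannot count new-onset disease against resolution, so net benefit may be overstated if new cases occur

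*Combined protocol and SAP*

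**What the plan says.** Section 3.7.2 lists 11 comorbidities as secondary efficacy variables and states that "the status of the comorbid conditions will be classified as unchanged, improved, resolved, or worsened". For the McNemar test it then forms two groups: unchanged with worsened, and resolved with improved. Section 3.7.6 sets the hypothesis: "The null hypothesis is that there is no change in each co-morbidity post surgery". The alternative there is a change in either direction. Neither section says whether subjects free of a condition at baseline enter its test, or how a new case is coded.

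On follow-up, section 3.4.5.1 says "Weight loss, status of pre-operative comorbidities and development of complications will be reviewed at every follow-up visit" and adds "This will include testing to follow pre-operative comorbidities". It limits scheduled repeat OGTT, at 1 and 5 years, to subjects with impaired glucose tolerance at baseline. The same section also provides for testing without regard to baseline disease: "Baseline laboratory and nutritional parameters will be repeated every 3 months for the first year post op" and "All laboratory, gastrointestinal, EKG, nutritional, and psychiatric evaluations which were performed at baseline will be repeated every 12 months".

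**The concern.** A test of no change in a comorbidity has to let cases appear as well as disappear. The 3.7.2 scale is written for subjects who already have the condition, and its grouping puts the one class that could hold a new case together with subjects in whom nothing happened.

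The study has no control arm, so the within-subject comparison is its only evidence on comorbidities, and comorbidity status is the first item of the secondary objective (2.2). New cases are plausible. Subjects enter at 14 to 17 and are followed for five years, to about 19 to 22. Reflux is a listed comorbidity, and 3.4.5.2 has subjects evaluated for removal of band fluid if they "develop symptoms such as heartburn, nausea, vomiting or overeating". If resolved cases count and new ones do not, a condition whose prevalence barely moves could be reported as significantly improved.

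**Working it through.** **Step 1. Follow each kind of subject through the rules.** The third and fourth columns apply 3.7.2. The last shows a McNemar table built on presence at baseline against presence at the visit.

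| Baseline | Visit | Class in 3.7.2 | McNemar group in 3.7.2 | Paired presence/absence |
|---|---|---|---|---|
| present | absent | resolved | resolved/improved | discordant, *b* |
| present | present, milder | improved | resolved/improved | concordant |
| present | present, same or more severe | unchanged or worsened | unchanged/worsened | concordant |
| absent | absent | unchanged, if rated | unchanged/worsened | concordant |
| absent | present | none stated; worsened is nearest | unchanged/worsened | discordant, *c* |

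Under 3.7.2 the last two rows fall in the same group, so *c* is never seen. Only a paired presence/absence table sets *c* against *b*.

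**Step 2. Size, with assumed counts.** The documents give no prevalence, resolution or new-onset figure, so there is no plan figure to reproduce. Inputs: 120 subjects (the maximum in 3.1); assumed, 30 with a condition at baseline, 15 of them resolved, and *c* new cases among the other 90.

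- Exact two-sided McNemar: p = 2 × P(X ≤ min(*b*, *c*)), X ~ Binomial(*b* + *c*, 0.5), capped at 1.
- Cases at the visit = 30 − 15 + *c*. Net fall = (15 − *c*)/120.

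| New cases *c* (of 90) | *b* : *c* | Exact p | Cases, before to after | Net fall, points |
|---|---|---|---|---|
| 0 | 15 : 0 | 2 × 0.5^15 = 0.00006 | 30 to 15 | 12.5 |
| 5 (6%) | 15 : 5 | 0.041 | 30 to 20 | 8.3 |
| 9 (10%) | 15 : 9 | 0.31 | 30 to 24 | 5.0 |
| 14 (16%) | 15 : 14 | 1.0 | 30 to 29 | 0.8 |

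The first row is also what is obtained when new cases occur but are not counted.

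**Step 3. A wider range, also assumed.** With N = 120, baseline prevalence of 10 to 30%, resolution of 30 to 50% and new onset of 2 to 10%, omitting new cases overstates the net fall by *c*/120. Here *c* runs from 2 to 11, so the overstatement is 2/120 = 1.7 to 11/120 = 9.2 points. At 20% prevalence (24 subjects) and 50% resolved (12), p is 0.0005 with new cases omitted. It is 0.013 with 2 new cases, 0.14 with 5 and 0.83 with 10. Not every setting changes the conclusion: at 30% prevalence and 50% resolved (18 of 36), 4 new cases still give p = 0.004.

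**Step 4. Would the data exist?** Mostly yes. Laboratory panels, esophagram, EKG and psychiatric instruments are repeated in all subjects. Table I has a comorbidity and medication row at 1 year, at the 6-monthly visits and at the yearly visits. Section 3.7.7 collects intercurrent illness and changes in weight-related conditions, and 3.6.1 records all adverse events. Detection is weaker where testing depends on baseline status or on indication: OGTT is limited as described, although abnormal HbA1c or fasting glucose or new symptoms prompt further testing, and sleep studies are done only if indicated. Blood pressure is a baseline item (3.4.3), but no follow-up reading is listed in 3.4.5.1 or Table I, although 3.7.2 judges hypertension by its change.

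**The case against.** The strongest reply is that the plan leaves a coding rule open and excludes nobody. New disease is looked for in all subjects. Band-related reflux would be caught as a complication at each visit, as an adverse event, and on the annual esophagram. A new case can be coded *worsened*. A McNemar test on presence and absence would count it in the off-diagonal cell. The 15 : 0 comparison comes from a table that 3.7.2 does not specify, with invented counts.

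Much of this stands, and it rules out several stronger readings that a reader might infer:

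- *New conditions go unrecorded, or follow-up testing in general is confined to pre-operative disease.* The routine testing in 3.4.5.1, Table I, 3.7.7 and 3.6.1 say otherwise.
- *Each comorbidity is analysed only in subjects who had it at baseline.* Neither 3.7.2 nor 3.7.6 sets that denominator.
- *The problem holds however the McNemar table is built.* It does not; a presence/absence table in all subjects removes it.
- *Blood pressure is not measured after surgery.* The documents show only that no reading is listed. Physical examinations are scheduled, and weight has no row in Table I either.
- *The data-sharing request for "New medical problems" shows what this trial's analysis omits.* That field belongs to a multi-site pooling project and says little about this analysis.

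The reply fails on its main point. Coding a new case as *worsened* does not help, because 3.7.2 pools that class with *unchanged*. The presence/absence test that would count it is not the one 3.7.2 describes: its categories are grouped change ratings. Adverse event summaries would show new cases but would not net them against resolutions.

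**Conclusion.** The point holds as a defect of classification and analysis on a secondary endpoint. As written, 3.7.2 gives new-onset disease no class, and its grouping ensures that a new case cannot count against a resolved one when the null in 3.7.6 is tested.

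A reader might go further and say that comorbidity benefit *is* overstated. The documents support only *may be*: the bias is zero without new cases, and no rates are given. Under the assumed ranges it is 1.7 to 9.2 percentage points of net fall, enough in some settings to turn a significant result into a non-significant one. The p-values describe a paired presence/absence test with and without its new-onset cell; they do not predict this trial's result. Nor would counting new cases remove regression to the mean or spontaneous remission, which come with the single-arm design.

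**What to change.** - **3.7.2:** add a *new onset* class. Stop using the grouping of unchanged/worsened against resolved/improved as the McNemar input. State for each of the 11 comorbidities what counts as present at a visit.
- **3.7.6:** for each comorbidity, run McNemar on presence at baseline against presence at the visit, in all implanted subjects with data. Beside percent resolved, report new-onset n/N among those free of the condition at baseline, with an exact 95% CI. Keep improved and worsened as descriptive counts, since change in severity without resolution does not enter this test.
- **3.4.5.1 and Table I:** word the visit review to cover every comorbidity listed in 3.7.2, whether or not present before surgery, and list the follow-up blood pressure reading on which 3.7.2 already relies.

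The cost is protocol and analysis wording, a presence definition for each condition and one more status code on the case report form. Most of the data are already collected. The downside is that reported benefit may be less favourable for some conditions.

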3.4.5.2 Band Adjustments

Fluid will be added to or removed from the band as indicated by the clinical progress, physical examination, and esophagram done at follow-up visit.

The adjustments will be performed as per study device manufacture's DFU.

Visits for band adjustments can also be initiated by the patient or their course between scheduled visits. If they lose weight too quickly; develop symptoms such as heartburn, nausea, vomiting or overeating; or develop a condition or illness requiring them to eat more, they will be evaluated for removal of fluid from the band. If they lose weight too slowly or overeat, they will be evaluated for addition of fluid to the band. Each evaluation will involve review of their clinical progress, physical examination, and esophagram if necessary.

